### 7.2 Secondary Endpoints

Effectiveness:

- Mean and changes in mean IOP and number of topical IOP-lowering medications from preoperative baseline over time
- Change from baseline (medicated) in mean IOP and mean number of topical IOP-lowering medications at Month 12
- Proportion of eyes achieving specific IOP targets ( $\leq 18$  mm Hg,  $\leq 17$  mm Hg,  $\leq 16$  mm Hg,  $\leq 15$  mm Hg,  $\leq 14$  mm Hg,  $\leq 13$  mm Hg, and  $\leq 12$  mm Hg at Month 12)
- Proportion of eyes achieving specific percentage IOP lower targets from baseline ( $\geq 25\%$  to  $50\%$  in  $5\%$  increments)
- Proportion of eyes achieving  $\geq 20\%$  IOP reductions and specific IOP targets detailed above on same or lower number of topical IOP-lowering medications at Month 12
- Mean and changes in mean IOP and number of topical IOP-lowering medications from preoperative baseline over time in eyes with medicated baseline IOP  $\leq 18$  mm Hg
- Needling rates; number of needlings per eye; outcomes post needling, including mean IOP and number of medications measured by proportion of eyes achieving  $>20\%$  reduction at Month 12 on same or fewer topical IOP-lowering medications, and number of subjects not using any topical IOP-lowering medications; and antifibrotic use during needling.

Complete and qualified success:

- Complete success (IOP  $\leq 18$  mm Hg, with  $20\%$  or greater IOP lowering from medicated baseline on no topical medications) at Month 12 (eyes with clinical hypotony will be excluded)
- Qualified success (IOP  $\leq 18$  mm Hg with  $20\%$  or greater IOP lowering from medicated baseline with topical medications) at Month 12 (eyes with clinical hypotony will be excluded)

- Medication-free eyes, mean IOP in this cohort, and proportion of eyes at specific IOPs ( $\leq 18$  mm Hg,  $\leq 17$  mm Hg,  $\leq 16$  mm Hg,  $\leq 15$  mm Hg,  $\leq 14$  mm Hg,  $\leq 13$  mm Hg, and  $\leq 12$  mm Hg at Month 12)
- Proportion of eyes achieving specific percentage IOP lower targets from baseline ( $\geq 25\%$  to  $50\%$  in  $5\%$  increments) with medication-free eyes.

Intraoperative adjunctive antifibrotic therapy administered:

- Compound/product, mode of administration, dose and concentration, timing of adjunctive agent (surgery day and pre- and postsurgical procedure/implantation).

Visual parameters recovery post surgery:

- BCVA with current glasses (preoperative and postoperative Day 1; Weeks 1 and 2; and Months 1, 3, 6, 9, and 12)

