1.2. Study Design

This is a post-marketing, multi-center, randomized, parallel group, prospective, open-label clinical trial to evaluate the ability of XEN to reduce IOP and reduce the amount of topical IOP-lowering medications in participants poorly controlled on topical therapy.

Participants will be randomized at a ratio of 2:1, resulting in approximately 68 eyes being implanted with XEN and approximately 34 eyes will receive trabeculectomy. A randomized study design was chosen because it prevents selection bias in treatment assignments and it produces comparable groups. This study will include participants presenting with glaucoma poorly controlled on topical therapy who are candidates for a subconjunctival drainage procedure. Participants will be screened for enrollment and eligible candidates will be approached to ascertain interest in study participation.

Participants can be enrolled into one of the following groups:

Group 1: XEN implanted (XEN group)

Group 2: Trabeculectomy (Trab group)

All inclusion/exclusion criteria, effectiveness endpoints, success rate, and follow up exams will be identical for both groups.

At baseline, participants with glaucoma not at target IOP when using at least 1 topical IOP lowering medication will be screened for eligibility to participate in the study. After the participant is determined to be eligible for participation in the study and is enrolled, the physician may stop the previously prescribed medications 1-4 weeks before surgery and begin preoperative medications (e.g., steroids, antibiotics, artificial tears, oral CAIs) to prepare the ocular surface before surgery. The detection and treatment of comorbid conditions, particularly diseases of the ocular surface disease (dry eye) and blepharitis, can help reduce eye inflammation (Baudouin, 2012). Stopping or reducing IOP lowering medications and replacing them, if necessary, with oral acetazolamide prior to surgery may be considered along with use of topical steroids and preservative-free lubricants to reduce ocular surface inflammation and improve the likelihood of successful implantation (Vera et al, 2018).

CONFIDENTIAL

Draft Statistical Analysis Plan v2.0

XEN-45 Gel Stent

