 - $\geq 20\%$ IOP reductions at Month 12
 - IOP value of ≤ 15 mmHg at Month 12
 - Same or lower in number of topical IOP-lowering medications at Month 12 compared to the baseline
- Proportion of participants meeting all following criteria:

CONFIDENTIAL

Draft Statistical Analysis Plan v2.0

XEN-45 Gel Stent

- $\geq 20\%$ IOP reductions at Month 12
- IOP value of ≤ 14 mmHg at Month 12
- Same or lower in number of topical IOP-lowering medications at Month 12 compared to the baseline
- Proportion of participants meeting all following criteria:
 - $\geq 20\%$ IOP reductions at Month 12
 - IOP value of ≤ 13 mmHg at Month 12
 - Same or lower in number of topical IOP-lowering medications at Month 12 compared to the baseline
- Proportion of participants meeting all following criteria:
 - $\geq 20\%$ IOP reductions at Month 12
 - IOP value of ≤ 12 mmHg at Month 12
 - Same or lower in number of topical IOP-lowering medications at Month 12 compared to the baseline
- Needling rates, number of needlings per eye, outcomes post needling, including mean IOP and number of medications measured by proportion of eyes achieving $>20\%$ reduction at 12 months on same or fewer topical IOP-lowering medications, and number of patients not using any topical IOP-lowering medications, antifibrotic use during needling

Complete and qualified success:

- Proportion of participants with complete success at Month 12 which is defined as meeting all following criteria in the study eye
 - IOP ≤ 18 mmHg at Month 12
 - $\geq 20\%$ reduction in IOP from medicated baseline, which is the IOP value at Baseline Qualifying Visit, at Month 12
 - No topical medications at Baseline Qualifying Visit
 - No clinical hypotony

The topical medication includes any topical ophthalmic medication used on the study eye regardless of the indication and dosage.

This endpoint will be analyzed among the participants without topical medication at Baseline Qualifying Visit.

- Proportion of participants with qualified success at Month 12 which is defined as meeting all following criteria in the study eye
 - IOP ≤ 18 mmHg at Month 12
 - $\geq 20\%$ reduction in IOP from medicated baseline, which is the IOP value at Baseline Qualifying Visit, at Month 12
 - Taking topical medications at Baseline Qualifying Visit
 - No clinical hypotony

CONFIDENTIAL

Draft Statistical Analysis Plan v2.0

XEN-45 Gel Stent

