The topical medication includes any topical ophthalmic medication used on the study eye regardless of the indication and dosage.

This endpoint will be analyzed among the participants with topical medication at Baseline Qualifying Visit.

- Proportion of participants with IOP value of ≤ 18 mmHg at Month 12 in medication-free eye
- Proportion of participants with IOP value of ≤ 17 mmHg at Month 12 in medication-free eye
- Proportion of participants with IOP value of ≤ 16 mmHg at Month 12 in medication-free eye
- Proportion of participants with IOP value of ≤ 15 mmHg at Month 12 in medication-free eye
- Proportion of participants with IOP value of ≤ 14 mmHg at Month 12 in medication-free eye
- Proportion of participants with IOP value of ≤ 13 mmHg at Month 12 in medication-free eye
- Proportion of participants with IOP value of ≤ 12 mmHg at Month 12 in medication-free eye

- Proportion of eyes achieving specific percentage IOP lower targets from baseline (≥ 25 -50% in 5% increments) with medication-free eyes

Note: medication-free eye at Month 12 is defined as no IOP-lowering medication was used to the study eye at Month 12.

Intraoperative adjunctive antifibrotic therapy administered:

- Compound/product, mode of administration, dose and concentration, timing of adjunctive agent (surgery day and pre- and postsurgical procedure/implantation)

Note: The data will be presented only if they are collected on CRF.

Visual parameters recovery post surgery:

- Mean and mean change in best corrected visual acuity (BCVA) with current glasses (preoperative and postoperative Day 1, Weeks 1 and 2, and Months 1, 3, 6, 9, and 12)
- Mean and mean change in manifest refraction (baseline and postoperative Months 1, 3, 6, and 12)
- Mean and mean change in surgically induced astigmatism (autorefractor reading [preoperative and postoperative Months 1, 6, and 12] and, at selected sites, topography [preoperative and postoperative Week 1 and Months 1 and 12])
- Mean and mean change in optical biometry (anterior chamber depth and keratometric values [preoperative and postoperative Day 1 and Week 2]) at selected sites.

CONFIDENTIAL

Draft Statistical Analysis Plan v2.0

XEN-45 Gel Stent

Other:

- Bleb photography (anterior segment optical coherence tomography [AS-OCT] and slit lamp photography at selected sites).

Safety:

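### Complete and qualified success count any eye drop as topical medication, while medication-free eyes count only IOP-lowering drugs; the conflict is masked until medication is read at Month 12

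*SAP*

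**What the plan says.** Protocol 7.2 defines complete success at Month 12 as IOP of 18 mm Hg or less with at least 20% "IOP lowering from medicated baseline on no topical medications". Qualified success is the same with topical medications. Neither definition says IOP-lowering. SAP 1.1.3 repeats this wording.

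SAP 5.4.2 adds three things:

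- **A drug definition**, given once under each endpoint: "The topical medication includes any topical ophthalmic medication used on the study eye regardless of the indication and dosage".
- **A visit for the medication test.** Complete success requires "No topical medications at Baseline Qualifying Visit"; qualified success requires "Taking topical medications at Baseline Qualifying Visit".
- **Denominators split at that same visit.** For complete success: "This endpoint will be analyzed among the participants without topical medication at Baseline Qualifying Visit". For qualified success: "This endpoint will be analyzed among the participants with topical medication at Baseline Qualifying Visit".

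For the medication-free analyses that follow, the section uses a different rule: "medication-free eye at Month 12 is defined as no IOP-lowering medication was used to the study eye at Month 12".

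SAP 1.1.4 adds time to complete success and time to qualified success. It refers to Section 1.1.3, not 5.4.2, for their definitions. SAP 5.5 analyses them by Kaplan-Meier.

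**The concern.** The trial compares IOP and the number of topical IOP-lowering medications. The primary endpoint counts IOP-lowering drugs, and protocol 10.1.1.2 lists IOP-lowering classes for the endpoints that count medications. In that setting, complete against qualified success would normally separate pressure control without glaucoma drops from control with them. Under the any-drop rule, lubricant, steroid, antibiotic or allergy drops count equally.

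Such drops are foreseen. SAP 1.2 allows "use of topical steroids and preservative-free lubricants to reduce ocular surface inflammation" before surgery. The postoperative adverse event list in the protocol refers to a medication taper after surgery, to blepharitis and to dysesthetic bleb.

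If the any-drop rule is applied to medication status after surgery, qualified success mixes eyes that need pressure-lowering drugs with eyes that need only surface care. Complete success is then understated. Both endpoints would also disagree with the medication-free results, which the protocol lists under the same heading.

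**Working it through.** The plan states no figure on this point, so there is none to reproduce. The check is to classify eyes under each combination of visit and drug definition.

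**Inputs**

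- Drug definition, visit and denominators: SAP 5.4.2, quoted above.
- Eligibility: inclusion criterion 6 (protocol 8.3.2) requires at least one topical IOP-lowering medication. Footnote b of protocol Table 8.1 makes the Baseline Qualifying Visit IOP a medicated value.
- Medication-free rule: SAP 5.4.2, IOP-lowering drugs only, at Month 12.

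**Set-up.** Take eyes that meet the IOP limit, the 20% reduction and the no-hypotony condition. Let an IOP-lowering drop and a lubricant each be present or absent, at the Baseline Qualifying Visit (BQV) and at Month 12. That gives 2 × 2 × 2 × 2 = 16 states. Eligibility fixes the IOP-lowering drop as present at the BQV, which leaves 8. Each row below covers two of them, with and without lubricant at the BQV; the result is the same for both.

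| Drops at Month 12 | BQV, any drop (SAP as written) | BQV, IOP-lowering only | Month 12, any drop | Month 12, IOP-lowering only | Medication-free under SAP |
|---|---|---|---|---|---|
| None | qualified | qualified | complete | complete | yes |
| Lubricant only | qualified | qualified | **qualified** | **complete** | yes |
| IOP-lowering only | qualified | qualified | qualified | qualified | no |
| Both | qualified | qualified | qualified | qualified | no |
| Complete, of 8 states | 0 | 0 | 2 | 4 | |

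These are counts of logical states, not expected proportions of eyes.

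**Reading the table**

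1. As written, every eligible eye that meets the other criteria is a qualified success, including one on no drops at Month 12. The visit causes this, not the drug definition: narrowing the definition alone leaves 0 of 8.
2. Moving the visit alone leaves the lubricant-only eye as qualified while the same section calls it medication-free. The drug definition decides 4 − 2 = 2 of the 8 states.
3. Only both changes together make complete success agree with medication-free status.

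**Time to success.** SAP 1.1.3 carries no BQV condition, so the masking in step 1 does not carry over to the Kaplan-Meier endpoints. If no topical medications is read literally, or with the meaning given in 5.4.2, a steroid or lubricant drop used after surgery can delay or block the complete-success event.

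**Illustration of size, assuming Month 12 status and all eyes in the arm as denominator.** Let p be the true complete-success rate and u the share of those eyes using a non-glaucoma drop. The observed rate is p × (1 − u). Both values are assumed: p = 0.50 and u from 0.10 to 0.30.

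- u = 0.10: 0.50 × 0.90 = 0.45
- u = 0.30: 0.50 × 0.70 = 0.35

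If u were 0.30 in one arm and 0.10 in the other, with p equal, a spurious difference of 0.45 − 0.35 = 10 points would appear.

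**The case against.** The strongest reply is that the sentence does nothing in 5.4.2 as it stands. That is correct. A reader might infer that an eye at 12 mm Hg on lubricant alone at Month 12 is moved from complete to qualified success by the any-drop rule. The documents do not support this: that eye is qualified because it was on an IOP-lowering drop at the Baseline Qualifying Visit, and drops at Month 12 are not examined.

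Second, the protocol leaves the drug class open. Neighbouring bullets in 7.2 specify IOP-lowering medications and these two do not, so the SAP's reading is literal and contradicts nothing in the protocol. This also stands. What remains is the conflict inside SAP 5.4.2, where two rules for closely related endpoints give different answers for the same eye.

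Third, applying the any-drop meaning to the Kaplan-Meier analyses is an inference, since 1.1.3 does not contain that sentence. True, but 1.1.3 offers no narrower meaning, and 5.4.2 holds the only explanation of the term in the SAP.

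Fourth, a reader might infer a bias between the arms. The documents give no rate of non-glaucoma drop use at Month 12 and no sign that it differs by procedure, and the use described in SAP 1.2 is before surgery. The 10-point figure shows only what an assumed imbalance would do.

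Finally, the stakes are limited. The primary endpoint counts IOP-lowering drugs only, and the SAP names no key secondary endpoint. IOP targets in medication-free eyes are reported separately, although without the combined success criteria.

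**Conclusion.** The point holds as an inconsistency of definition with a conditional effect. SAP 5.4.2 uses two incompatible meanings of medication for closely related endpoints. In the 5.4.2 proportions the conflict is hidden by the larger problem that medication is tested at baseline, which leaves complete success empty apart from any eye enrolled in breach of criterion 6. It takes effect when that is corrected, and possibly already in SAP 5.5. A sponsor who corrected only the visit would still misclassify every otherwise successful eye on non-glaucoma drops alone.

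The size cannot be estimated from the documents. The fall from 50% to between 45% and 35% rests on assumed rates and applies only after the visit is corrected. The affected endpoints are secondary and exploratory; the primary conclusion is untouched. The change is worth making because it is cheap and because correcting the visit is incomplete without it.

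**What to change.** In SAP 5.4.2, replace the drug-definition sentence under both complete and qualified success with: *Topical medication means topical IOP-lowering medication used on the study eye.* State the same in 5.5 for the two time-to-success endpoints.

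In the same revision, move the medication test and the denominators in 5.4.2 from the Baseline Qualifying Visit to Month 12, in line with protocol 7.2 and SAP 1.1.3, and state the denominator explicitly. Neither change is sufficient alone: the first by itself reclassifies no eligible eye, and the second by itself leaves the lubricant-only eye misclassified.

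The cost is wording in three places and a filter on IOP-lowering drugs in the concomitant medication records, which the primary endpoint already requires. No new data are needed. If the sponsor also wants to report freedom from all eye drops, that can be a separately named descriptive summary.

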### 8.3.2 Inclusion Criteria

To be eligible for study entry subjects must satisfy all of the following criteria in the study eye (only 1 eye will be allowed in the study):

1. Male or female subjects ages  $\geq 18$  years
2. Able to provide signed written informed consent
3. Glaucoma in which the IOP is not controlled on current topical IOP-lowering glaucoma medication
4. Best-corrected baseline Snellen visual acuity of 20/100 or better
5. Visual field mean deviation no worse than -18.0 dB (with no dense paracentral scotomas, eg,  $>18$  dB total deviation on 1 or more of the 4 paracentral points)
6. Medicated IOP  $\geq 15$  mm Hg and  $\leq 44$  mm Hg on at least 1 topical IOP-lowering medication
7. Subjects not anticipated to require any other ocular surgery (eg, cataract surgery) in either eye up to 3 months from the time of inclusion
8. Area of healthy, free, and mobile conjunctiva in the target area, ie, superior bulbar conjunctiva
9. Visible trabecular meshwork with Shaffer angle grade  $\geq 2$  in the target area or, in eyes with prior failed angle surgery, an open angle in the target area
10. Preoperative laser trabeculoplasty is allowed 3 or more months prior to randomization
11. Failed ab-interno canal or suprachoroidal MIGS procedures (such as i-Stent®, gonioscopy-assisted transluminal trabeculotomy [GATT], ab-interno canaloplasty [ABiC™], Kahook Dual Blade goniotomy, etc) are allowed 3 or more months before enrollment, with the exception of CyPass® Micro-Stents, which are not allowed. Ab-interno ablative procedures (such as endoscopic cyclophotocoagulation [ECP]) are also allowed 3 or more months before enrollment.

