#### **8.4.5 Prior and Concomitant Therapy**

Topical IOP-lowering medication may be stopped 1 to 4 weeks before surgery and re-started according to the investigator's recommendation. At baseline, subjects are to be using at least 1 topical IOP-lowering medication and, when using that medication at the maximum tolerated dose, their IOP is not controlled. After the subject is determined to be eligible for participation in the study and is enrolled, the physician may stop the previously prescribed medications 1 to 4 weeks before surgery and begin preoperative medications (eg, steroids, antibiotics, artificial tears) to prepare the ocular surface before surgery. The detection and treatment of comorbid conditions, particularly diseases of the ocular surface disease (dry eye) and blepharitis, can help reduce eye inflammation (Baudouin 2012). Stopping or reducing IOP-lowering medications and replacing them, if necessary, with oral acetazolamide prior to surgery may be considered along with use of topical steroids and preservative-free lubricants to reduce ocular surface inflammation and improve the likelihood of successful implantation (Vera et al. 2018).

Subjects who have had prior ab-externo incisional glaucoma surgery (such as trabeculectomy, viscocanalostomy, canaloplasty, tube shunts of any type, collagen implants, etc), conjunctival filtering surgery (such as XEN), transscleral cycloablative procedures (such as cyclophotocoagulation, micropulse cyclophotocoagulation, cryotherapy, UC3, etc) or prior major conjunctival surgery (ie, scleral buckle) are not eligible for the study (see Section 8.3.3).

Perioperative adjunctive antifibrotic therapy should be used according to physician training and practice.

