1.1.3. Secondary Endpoints

Effectiveness:

- Mean and changes in mean IOP and number of topical IOP-lowering medications from preoperative baseline over time
- Change from baseline (medicated) in mean IOP and mean number of topical IOP-lowering medications at Month 12
- Proportion of eyes achieving specific IOP targets (≤ 18 mm Hg, ≤ 17 mm Hg, ≤ 16 mm Hg, ≤ 15 mm Hg, ≤ 14 mm Hg, ≤ 13 mm Hg, and ≤ 12 mm Hg at Month 12)
- Proportion of eyes achieving specific percentage IOP lower targets from baseline ($\geq 25\%$ to 50% in 5% increments) over time
- Proportion of eyes achieving $\geq 20\%$ IOP reductions and specific IOP targets detailed above on same or lower number of topical IOP-lowering medications at Month 12
- Mean and changes in mean IOP and number of topical IOP-lowering medications from preoperative baseline over time in eyes with medicated baseline IOP ≤ 18 mm Hg
- Needling rates; number of needlings per eye; outcomes post needling, including mean IOP and number of medications measured by proportion of eyes achieving $>20\%$ reduction at Month 12 on same or fewer topical IOP-lowering medications, and number of subjects not using any topical IOP-lowering medications; and antifibrotic use during needling.

Complete and qualified success:

- Complete success (IOP ≤ 18 mm Hg, with 20% or greater IOP lowering from medicated baseline on no topical medications) at Month 12 (eyes with clinical hypotony will be excluded)
- Qualified success (IOP ≤ 18 mm Hg with 20% or greater IOP lowering from medicated baseline with topical medications) at Month 12 (eyes with clinical hypotony will be

CONFIDENTIAL

Draft Statistical Analysis Plan v2.0

XEN-45 Gel Stent

excluded)

- Medication-free eyes, mean IOP in this cohort, and proportion of eyes at specific IOPs (≤ 18 mm Hg, ≤ 17 mm Hg, ≤ 16 mm Hg, ≤ 15 mm Hg, ≤ 14 mm Hg, ≤ 13 mm Hg, and ≤ 12 mm Hg at Month 12)
- Proportion of eyes achieving specific percentage IOP lower targets from baseline ($\geq 25\%$ to 50% in 5% increments) with medication-free eyes.

Intraoperative adjunctive antifibrotic therapy administered:

- Compound/product, mode of administration, dose and concentration, timing of adjunctive agent (surgery day and pre- and postsurgical procedure/implantation).

Visual parameters recovery post surgery:

- Mean and mean change in best corrected visual acuity (BCVA) with current glasses (preoperative and postoperative Day 1; Weeks 1 and 2; and Months 1, 3, 6, 9, and 12)

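### SAP 5.4.2 reads medication use for complete and qualified success at the Baseline Qualifying Visit, not at Month 12, which leaves complete success with no denominator and makes qualified success a pooled rate

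*SAP*

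**What the plan says.** Protocol 7.2 (repeated in the Synopsis) defines complete success as IOP of 18 mm Hg or less with at least 20% "IOP lowering from medicated baseline on no topical medications) at Month 12 (eyes with clinical hypotony will be excluded". Qualified success is the same result with topical medications. SAP 1.1.3 keeps this definition: "with 20% or greater IOP lowering from medicated baseline on no topical medications) at Month 12".

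SAP 5.4.2, which sets out the endpoints for analysis, keeps the Month 12 pressure criteria but makes the medication criterion none (complete) or some (qualified) at the Baseline Qualifying Visit. It then limits each denominator in the same way:

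- Complete success: "This endpoint will be analyzed among the participants without topical medication at Baseline Qualifying Visit".
- Qualified success: "This endpoint will be analyzed among the participants with topical medication at Baseline Qualifying Visit".

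The scope of medication is broad: "The topical medication includes any topical ophthalmic medication used on the study eye regardless of the indication and dosage".

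On entry, inclusion criterion 6 (Protocol 8.3.2) requires a medicated IOP in range "on at least 1 topical IOP-lowering medication". Protocol 8.4.5 repeats the requirement: "At baseline, subjects are to be using at least 1 topical IOP-lowering medication".

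**The concern.** The two documents, and two sections of the SAP, give the same endpoint names different meanings. A programmer working from 5.4.2 would look for complete successes among eyes that eligibility keeps out of the trial. The same programmer would count as qualified successes all eyes that meet the pressure and hypotony criteria, whether or not they still need drops.

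Whether pressure control is achieved without drops is what the complete/qualified split is meant to show. As 5.4.2 stands, one half of the split cannot be reported, and the other half would look like a normal result while carrying the wrong label. SAP Appendix 2, on changes to protocol-planned analyses, mentions only the sample size reduction, so nothing marks this as a deliberate change.

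**Working it through.** **1. The definitions side by side**

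| Element | Protocol 7.2 and SAP 1.1.3 | SAP 5.4.2 |
|---|---|---|
| IOP cut-off and 20% reduction | Month 12 | Month 12 |
| Medication status | Month 12 | Baseline Qualifying Visit |
| Denominator | not restricted by baseline medication | split by baseline medication |
| Clinical hypotony | eyes excluded | absence is a success criterion |

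**2. Who can enter the complete-success denominator**

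- Inclusion criterion 6 and Protocol 8.4.5 put every eligible eye on one or more topical pressure-lowering drugs at baseline.
- Footnote b of SAP Table 1-1 says the Baseline Qualifying Visit pressure is the medicated value, taken with the subject on treatment.
- Medication may be stopped before surgery only after eligibility and enrollment (Protocol 8.2.1 and 8.4.5, SAP 1.2), so stopping it does not alter status at that visit.
- SAP Section 4 requires Enrolled eyes to meet all entry criteria, and ITT is a subset of Enrolled.
- The broad medication scope narrows the group further, since any topical eye drug would disqualify an eye.

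The set is empty by design. The 5.4.2 definition also conflicts with itself: it measures "reduction in IOP from medicated baseline, which is the IOP value at Baseline Qualifying Visit, at Month 12" while requiring no medication at that same visit.

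**3. Planned denominators**

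SAP Section 3 plans 102 completers. With 70% success in both arms, a 24-point margin, 2:1 allocation, one-sided 5%, and 80% power carried over from the initial calculation, the trabeculectomy arm needs (1.645 + 0.842)² × (0.21 + 0.21/2) / 0.24² = 6.18 × 0.315 / 0.0576 = 33.8, so 34. XEN needs 68, for a total of 102, and 102/0.90 gives 114 to enroll (76 and 38). These figures serve here only as denominators.

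Under 5.4.2 the complete-success denominator is 0 of 68 and 0 of 34 planned completers (0 of 76 and 0 of 38 on the enrollment target). The proportion is 0/0. The 95% CI of the difference planned in SAP 5.4.2.1 does not exist.

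**4. What qualified success becomes**

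Let c and q be the complete and qualified rates under the Month 12 definition. Use one denominator, one medication scope, and count hypotony as non-success. SAP 5.4.2 then reports c + q as qualified success, and the arm difference becomes (c₁ − c₂) + (q₁ − q₂).

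Illustration, assuming 70% of eyes meet the pressure and hypotony criteria (the SAP's planning rate for the primary endpoint, borrowed here):

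| Drop-free share of successes | Complete, Month 12 | Qualified, Month 12 | Reported by 5.4.2 |
|---|---|---|---|
| 25% | 17.5% | 52.5% | qualified 70%, complete none |
| 50% | 35.0% | 35.0% | the same |
| 75% | 52.5% | 17.5% | the same |

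Now keep 70% in both arms and let the drop-free share differ (assumed; XEN then trabeculectomy). The interval is d ± 1.96 × √(c₁(1−c₁)/68 + c₂(1−c₂)/34).

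| Shares | Complete success | Difference (95% CI), points | Qualified difference in 5.4.2 |
|---|---|---|---|
| 60%, 80% | 42% vs 56% | −14 (−34.4 to 6.4) | 0 |
| 50%, 90% | 35% vs 63% | −28 (−47.8 to −8.2) | 0 |
| 40%, 90% | 28% vs 63% | −35 (−54.4 to −15.6) | 0 |

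If the shares are equal in the two arms, nothing is hidden.

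**5. Whether another endpoint fills the gap**

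SAP 5.4.2 also lists the composite of 18 mm Hg or less, 20% reduction and no more drops than at baseline; this admits medicated eyes. It lists pressure cut-offs in eyes that are medication-free at Month 12, but these carry no 20% criterion. The percentage-reduction targets in medication-free eyes start at 25% and carry no pressure cut-off. None is complete success.

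**The case against.** The strongest reply is about weight. The correct definition is already in SAP 1.1.3. SAP 5.4.1 names no key secondary endpoint, there is no multiplicity adjustment, and the primary endpoint has its own Month 12 medication rule in 5.3.1. The neighboring endpoints recover part of the information. Table specifications are in a separate document, and an empty row would probably be noticed. All of this stands and limits the seriousness. It does not cover the pooled qualified rate, which would look plausible.

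A reader might infer that a few eyes with deviations or missing medication records (SAP 6.3.3) would populate complete success and give a misleading estimate. The documents do not support this. An eye that fails the medication criterion is not Enrolled under SAP Section 4. A missing medication count is not the same as no medication. The list of major deviations has no entry for an eye off topical treatment. The argument rests on the empty set alone.

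A reader might also infer that the arms do differ in drop-free success. No document gives those rates, so the differences above show only what pooling could conceal.

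The broad scope of topical medication is not in itself an error: the protocol's wording for these two endpoints is not limited to pressure-lowering drugs.

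**Conclusion.** The point holds. As 5.4.2 is written, complete success cannot be estimated, and qualified success is the sum of the two protocol endpoints. The empty denominator follows from the entry criteria and the SAP's population definitions and needs no numerical assumption. The sum identity assumes a common denominator, one medication scope and hypotony counted as non-success. The hidden differences of 14 to 35 points rest on assumed rates.

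This should be fixed, but it does not threaten the trial's main conclusion: the endpoints are named in the protocol but non-key, and the primary analysis is unaffected. The SAP also holds two definitions of one term, because the time-to-success endpoints in 1.1.4 refer to 1.1.3 rather than 5.4.2.

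**What to change.** In SAP 5.4.2:

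1. Replace both baseline-visit medication criteria with status at Month 12: none for complete success, one or more for qualified success.
2. Delete the two sentences that restrict the denominators by baseline medication.
3. Use one common ITT denominator for both endpoints. Count eyes that Protocol 8.3.4 discontinues as failures after additional glaucoma surgery as non-successes even without Month 12 data, since a denominator of eyes with Month 12 data alone could drop them. Impute nothing else.
4. State one scope of topical medication and apply it to both endpoints. Limiting it to pressure-lowering drugs would match the Month 12 algorithm in 5.3.1 and the medication-free note in 5.4.2, but is optional.
5. Reconcile the hypotony wording: 1.1.3 excludes such eyes, whereas 5.4.2 makes absence of hypotony a success criterion. Say whether they leave the denominator or count as non-successes.
6. For the time-to-success endpoints (1.1.4 and 5.5), state that the same criteria apply with medication status at each visit. Month 12 status alone cannot date an event.

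Record the clarification in Appendix 2. The cost is SAP wording and programming. Month 12 pressure and concomitant medication are already collected, and the rule for Month 12 pressure-lowering medication is already written.
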